2.3 Treatment Assignment and Blinding

Approximately 60 subjects will be enrolled consecutively at approximately 7 study sites in Brazil. Recruitment will also target men, who are typically under-represented in aesthetic studies. Study treatments include:

- **BOTOX:** The dose and the number of injection points may be adapted to the needs of the subject, based on their characteristics and location of the muscles to be treated. Subjects will receive at least one BOTOX treatment in the following areas: glabellar lines (GLs), crow's feet lines (CFLs), and forehead lines (FHLs).
- **HArmonyCa Lidocaine:** The investigator will determine the appropriate volume to be injected during initial and touch-up treatments based on his/her clinical experience. The maximum total volume of HArmonyCa Lidocaine allowed per subject for the initial and touch-up treatment combined is 4 syringes (5 milliliter [mL]).
- **JUVÉDERM:** The investigator will determine the appropriate volume to be injected during initial and touch-up treatments based on his/her clinical experience.
 - JUVÉDERM VOLITE [REDACTED]: The maximum total volume of JUVÉDERM VOLITE [REDACTED] allowed per subject for the initial and touch-up treatments combined is 4 syringes (4 mL).
 - JUVÉDERM VOLBELLA with Lidocaine: The maximum combined total volume of JUVÉDERM VOLBELLA with Lidocaine allowed per subject for all facial areas treated for both the initial and touch-up treatments combined is 2 syringes (2 mL).
 - JUVÉDERM VOLIFT with Lidocaine: The maximum total volume of JUVÉDERM VOLIFT with Lidocaine allowed per subject for the initial and touch-up treatments combined is 4 syringes (4 mL).
 - JUVÉDERM VOLUMA with Lidocaine: The maximum total volume of JUVÉDERM VOLUMA with Lidocaine allowed per subject for the initial and touch-up treatments combined is 4 syringes (4 mL).

- JUVÉDERM VOLUX with Lidocaine: The maximum total volume of JUVÉDERM VOLUX with Lidocaine allowed per subject for the initial and touch-up treatments combined is 4 syringes (4 mL).

The investigator should not inject greater than 20 mL of filler (Juvéderm and HArmonyCa Lidocaine) per 60 kg (130 lbs.) body mass per year for a single subject.

Blinding and randomization are not applicable. This is an open-label, single-arm study. Subjects are enrolled consecutively based upon subject need and all subjects are intended to receive all treatments. Investigators will perform all treatments and evaluations.

2.4 Sample Size Determination

A sample size of 48 subjects will provide 90% power to detect if change from baseline to end of study visit in the FACE-Q™: Satisfaction with Facial Appearance Overall Scale Rasch-transformed score is different from zero, assuming a mean change of 12.0 and a standard deviation of 25.0.

This calculation is based on a one-sample, 1-sided t-test at 0.025 significance level. The assumptions of mean and standard deviation are based on FACE-Q™ results from the HARMONY Study GMA-CMB-14-001. Anticipating a potential 20% drop-out rate (for early withdrawals and/or subjects who failed to duly complete the FACE-Q™: Satisfaction with Facial Appearance Overall Scale assessment at end of study), 60 subjects will be enrolled.

PASS 2008 software was used to calculate the sample size.

3.0 Endpoints

3.1 Primary Efficacy Endpoint

The primary efficacy endpoint is the change from baseline in the overall Rasch-transformed score of the FACE-Q™: Satisfaction with Facial Appearance Scale to the final study visit (V7).

3.2 Secondary Efficacy Endpoints

3.2.1 Key Secondary Efficacy Endpoints

- Subject's assessment of aging appraisal as measured by the change from baseline in the Rasch-transformed score of the FACE-Q™: Aging Appraisal to final study visit (V7)

- Subject's assessment of psychological function as measured by the change from baseline in the Rasch-transformed score of the FACE-Q™: Psychological Function Scale to final study visit (V7)
- Subject's assessment of social function as measured by the change from baseline in the Rasch-transformed score of the FACE-Q™: Social Function Scale to final study visit (V7)
- Subject's assessment of satisfaction with skin as measured by the change from baseline in the Rasch-transformed score of the FACE-Q™: Satisfaction with Skin to final study visit (V7)
- Subject's assessment of age-related facial appearance by the Self-Perception of Age (SPA) measure at baseline to final study visit (V7); responders are defined as having achieved a younger category.

3.2.2 Other Secondary Efficacy Endpoints

- Investigator's assessment of global facial aesthetic improvement as measured by the 5-point Global Aesthetic Improvement Scale (GAIS) at final study visit (V7)
- Subject's assessment of global facial aesthetic improvement as measured by the 5-point GAIS at final study visit (V7)
- Change in subject's satisfaction with appearance of periorbital area as measured by the change from baseline in the Periorbital Aesthetic Appearance Questionnaire (PAAQ) to final study visit (V7)

3.3 Safety Endpoints

The safety endpoints will include the number and percentage of subjects who have any adverse events (AEs), injection site reactions (ISRs) or device deficiencies.

All AEs and injection site reactions (ISRs) will be collected from when the ICF is signed through to the last study visit (V7). Serious adverse events (SAEs) will be reported within the specified time and format directly to the Sponsor.

4.0 Analysis Populations and Subgroup

4.1 Analysis Populations

4.1.1 Modified Intent-to-Treat (mITT) Population

The mITT Population is defined as all subjects who enrolled and had at least one post-baseline efficacy assessment at V7.

4.1.2 Evaluable Population

The Evaluable Population is defined as all subjects in the mITT Population who received study products (JUVÉDERM and BOTOX) as treatments in this study, had at least one efficacy assessment at the final visit (V7), and had no significant protocol violations or deviations that will affect any efficacy endpoint. Such significant protocol violations or deviations will be determined during data review.

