#### 11.1.1 Analysis Populations

The following analysis populations will be used:

- mITT (modified Intent-to-Treat) Population - all subjects who enrolled and had at least one post-baseline efficacy assessment.
- Evaluable Population— all subjects as defined in the mITT Population who have received both study products as treatments in this study, had an efficacy assessment at the final visit (V7) and no major protocol violations or deviations.
- Safety Population – all subjects who received any product used as treatment in this study.

The mITT Population will be used for subject disposition, demographics and baseline characteristics summary, efficacy and the Safety Population will be used for safety analyses. The Evaluable Population will be used on key efficacy endpoints.

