## 11.4 Efficacy Analyses

Unless stated otherwise, all efficacy analyses will be based on the mITT and Evaluable Populations.

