8.0 Efficacy Analyses

8.1 General Considerations

- All efficacy analyses will be conducted in the Evaluable Population.
- Day 1 is defined as the day on which the study treatment is first received.
- Baseline for efficacy is defined as the last non-missing assessment on or prior to Day 1.
- Study day is relative to Day 1.
- Change from baseline will be computed as post-baseline minus baseline.

- Categorical variables will be summarized descriptively using number of subjects with observed values or events (n) and the percentage of subjects with observed values or events.
- Continuous variables will be summarized descriptively using number of subjects with observed values (n), mean, standard deviation (SD), standard error of mean (SEM), median, minimum (min), and maximum (max).
- Unless otherwise specified, the estimated mean and median for a set of values will be printed out to 1 more significant digit than the original values; the SD and SEM will be printed out to 2 more significant digits than the original values; the min and max will report the same significant digits as the original values.
- Shapiro-Wilks test will be used to check the normality assumption. If the normality assumption is met, the statistical hypothesis test will be performed based on one-sample, one-sided t-test at 0.025 significance level. If the normality assumption is not met, Wilcoxon signed-rank test will be used instead and a 97.5% confidence interval (CI) for the median will be presented using the Hodges Lehmann method. Shapiro-Wilks and Wilcoxon signed-rank test will be performed by proc univariate procedure, and Hodges Lehmann CI of the median for paired samples will be performed based on a SAS macro by Han (2008) [\[1\]](#) as specified in SPP Section 3.3.
- All CIs will be 1-sided 97.5% CIs, and will be printed to 2 decimal places, unless stated otherwise. P-values output will be in the format: ‘0.xxxx’, where xxxx is the value rounded to 4 decimal places. Every p-value less than 0.0001 will be presented as <0.0001. If the p-value is returned as >0.9999, then present it as it is.
- Unless otherwise specified, the summaries will be provided by treatment group, gender, and overall.

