Appendix A. Protocol Deviations and Violations

A protocol deviation (PD) is any non-adherence to study procedures that does not result in additional risk to the subject. Protocol deviations will be reviewed and documented before database lock.

A protocol violation (PV) is any non-adherence to the protocol that may result in significant additional risk to the subject (e.g., enrollment of a subject who does not meet the study criteria). A protocol violation can also be an event of non-adherence to Good Clinical Practice (GCP) that may impact subject safety (e.g., failure to obtain proper consent before performing study procedures). Violations should be reported to the study sponsor and the Institutional Review Board (IRB) within 5 working days if they occur.

Significant PDs/PVs (equivalent to major PDs/PVs as collected in data) will be identified before database lock. Significant PDs/PVs which impact the study conduct, data validity or integrity for the study outcomes will be summarized by the following categories:

- Inclusion or exclusion criteria
- Withdrawal Criteria
- Treatment
- Concomitant Medications
- Timeframe Deviation

The number and percentage of subjects with significant PDs/PVs will be summarized for the Safety Population by gender and total, and by treatment group and overall, for the Safety Population.

All PDs/PVs will be listed for the Safety Population.

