Appendix C. Changes to Protocol-planned Analyses

Protocol Planned Analysis	Modified Analysis
All efficacy analyses will be based on the mITT and Evaluable Populations.	All efficacy analyses will be based on the Evaluable Populations.
Subgroup analysis by gender and treatment touch-ups.	Subgroup analysis by gender only.
mITT (modified Intent-to-Treat) Population - all subjects who enrolled and had at least one post-baseline efficacy assessment.	mITT (modified Intent-to-Treat) Population - all subjects who enrolled and had at least one post-baseline efficacy assessment at V7.
Evaluable Population– all subjects as defined in the mITT Population who have received both study products as treatments in this study, had at efficacy assessment at the final visit (V7) and no major protocol violations or deviations.	Evaluable Population– all subjects as defined in the mITT Population who have received both study products as treatments in this study, had at efficacy assessment at the final visit (V7) and no major protocol violations or deviations that will affect any efficacy endpoint.
Exploratory efficacy analysis may be performed on the collected video and photographs.	Removed.

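### Which recorded major deviations remove a subject from the only efficacy population is judged at data review, and nothing in the SAP withholds V7 scores from those judging

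*SAP*

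**What the plan says.** Protocol 11.1.1 defines the Evaluable Population as mITT subjects who received the study products and who "had an efficacy assessment at the final visit (V7) and no major protocol violations or deviations". SAP 4.1.2 changes the last condition: subjects qualify if, among other things, they "had no significant protocol violations or deviations that will affect any efficacy endpoint". It then says how this is settled: "Such significant protocol violations or deviations will be determined during data review". SAP Appendix C discloses the change.

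SAP Appendix A sets two limits: "Significant PDs/PVs (equivalent to major PDs/PVs as collected in data) will be identified before database lock". It also gives five categories (eligibility criteria, withdrawal criteria, treatment, concomitant medications, timeframe). These serve to tabulate significant deviations; they do not say which ones exclude a subject.

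The population carries the whole efficacy result. Protocol 11.4 provides that, unless stated otherwise, "all efficacy analyses will be based on the mITT and Evaluable Populations". SAP 8.1 replaces this with "All efficacy analyses will be conducted in the Evaluable Population", and Appendix C confirms it. SAP 8.3.4 plans no additional analysis of the primary endpoint. SAP 2.3 states: "This is an open-label, single-arm study".

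**The concern.** A deviation recorded as major does not by itself settle membership under SAP 4.1.2. Someone must still decide, subject by subject, whether it affects an endpoint. The plan does not say who decides, by what criteria, or with which data in view. Database lock does not mask outcomes: there is no treatment code to break, and V7 questionnaires can be entered and readable before lock.

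The primary test asks whether the mean change in FACE-Q Satisfaction with Facial Appearance exceeds zero. With no control arm, any tendency to exclude deviators with poor change scores and keep those with good ones moves the mean and the test in the favourable direction, and nothing offsets it. Because the mITT efficacy analysis was dropped, no planned analysis would show the effect of the exclusions beside the main result.

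**Working it through.** **Inputs from the documents.** Protocol 11.7 and SAP 2.4: 48 evaluable subjects, mean change 12.0, SD 25.0, one-sample one-sided t-test at 0.025, 90% power, 60 enrolled for 20% dropout.

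**Inputs that are assumptions.** Neither document gives a deviation rate. I take 6 or 12 of the 48 subjects as having a recorded major deviation unrelated to outcome. Changes are normal with SD 25.

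**Step 1. The plan's own figure.** Noncentral t, 47 degrees of freedom, noncentrality (12/25) × √48 = 3.33: power is 90.3%. Enrolment is 48/(1 − 0.20) = 60. Both reproduce.

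**Step 2. Exclusion that ignores the outcome.** If every deviator is excluded, as the protocol's rule would do, simulated type I error stays at 2.5% with 10%, 20% or 30% of subjects deviating (200,000 trials each). Excluding deviators is not itself the problem.

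**Step 3. Exclusion that follows the outcome, true change zero.** Only deviators with a non-positive change are excluded; the rest are kept.
- The chance of a non-positive change is 0.5, so on average 3 of 6 deviators are excluded, or 6 of 12.
- The mean of an excluded change is −25 × √(2/π) = −19.9.
- Shift in the mean, roughly: 3 × 19.9/45 = +1.3 points with 6 deviators; 6 × 19.9/42 = +2.8 points with 12.
- Simulated type I error (200,000 trials): about 5% with 6 deviators, about 11% with 12.

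**Step 4. The same rule at the planned mean of 12, with 6 deviators.**
- The chance of a non-positive change is Φ(−12/25) = 0.316, so 6 × 0.316 = 1.9 subjects are excluded on average.
- The mean of an excluded change is 12 − 25 × φ(0.48)/Φ(−0.48) = −16.2, which is 28.2 below 12.
- Shift: 1.9 × 28.2/46.1 = about +1.2 points. Simulated power goes from 90% to 94%.

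**Step 5. Upper bound.** The lowest changes among all 48 are removed, true change zero (200,000 trials).

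| Lowest changes removed | Type I error | Shift in mean |
|---|---|---|
| 1 | about 6% | +1.2 |
| 2 | about 11% | +2.2 |
| 3 | about 17% | +3.2 |

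At the planned mean, removing the three lowest would make 12.0 read as about 15.2. This requires all three to have a recorded major deviation.

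**The case against.** The strongest reply is that the SAP already confines the judgement.

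- **The pool is limited.** Significant means major as collected, so a low scorer with no recorded major deviation cannot be removed, and nobody can be removed on a deviation first identified after lock. This stands. It makes the three-lowest case an upper bound and not an expectation.
- **The SAP criterion is narrower than the protocol's.** The protocol excludes for any major deviation; the SAP excludes only for those that affect an endpoint, so on its face it removes no more subjects. This also stands, but the discretion now lies in which major deviators to keep, which is the selection in Steps 3 and 4.
- **Selection would be detectable.** SAP 5.0 lists population membership for all screened subjects, Appendix A lists all deviations, and SAP 8.3.3 lists FACE-Q scores for the Safety Population. A reader of those listings could identify the excluded subjects and recompute the result. That is a real safeguard after the fact; it does not prevent the selection.
- **The scenarios are adversarial.** They assume every deviator with a non-positive change is removed and every other one kept. This is correct, and the figures should be read as what the rule allows.

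A reader might infer from the open-label design that the reviewers will have V7 FACE-Q scores in front of them. The documents do not say so. Open-label describes knowledge of treatment; neither document grants or bars access to questionnaire scores during deviation review. Only the absence of a restriction can be stated.

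**Conclusion.** The point holds as a gap in how membership of the sole efficacy population is decided. A case-by-case judgement on recorded major deviations is made before lock, with no requirement that the people making it lack V7 efficacy scores. The rule therefore permits outcome-dependent exclusion. To read it as evidence that exclusions were outcome-driven would go too far; nothing in the documents supports that.

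The Step 3 and Step 4 sizes depend on the assumed number of deviators and on fully selective exclusion. Type I error matters only if the true change is near zero. Under the planning assumptions the test would usually succeed anyway, and the practical harm is an overstated mean change of about a point in the 6-deviator case. This is an inexpensive improvement that should be made, not a flaw that undermines the design.

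**What to change.** In SAP 4.1.2 and Appendix A:

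1. State that excluding deviations are classified from a listing that carries no post-baseline FACE-Q, PAAQ, SPA or GAIS values, by reviewers who have not been given those values.
2. Require the list of excluded subjects, with reasons, to be signed and dated before database lock and before those reviewers receive V7 efficacy data.
3. Where they can be foreseen, name the excluding deviation types within the existing Appendix A categories.
4. As a check, also report the primary endpoint in the mITT Population, as the protocol planned. Because the SAP's mITT definition itself requires an efficacy assessment at V7, this shows the effect of deviation exclusions but does not address missing V7 data.

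The cost is SAP wording, one extra listing and one extra analysis, with less flexibility for an unforeseen deviation. No study procedure changes.

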4.1.3 Safety Population

The Safety Population is defined as all subjects who received any product as treatment in this study.

Unless otherwise specified, all efficacy analyses will be based on the Evaluable Population. The mITT Population will be used for demographics and baseline characteristics summary. The Safety Population will be used for the protocol deviation and violation, treatment exposure, all safety analyses, and listings unless otherwise specified.

4.2 Subgroup

Subgroup analysis will be performed for the primary efficacy analysis by gender, as male and female subjects may have differing expectations/perceptions of aesthetic improvement; they will be examined separately.

5.0 Subject Disposition and Treatment Disposition

The number and percentage of subjects who are in the mITT Population, Evaluable Population, and Safety Population will be summarized by treatment group (HArmonyCA, Non-HArmonyCA), gender (male, female), and overall, for all eligible subjects (subjects who signed the informed consent and met all eligibility criteria). Screen failure subjects and the reasons for screen failure will also be summarized by overall, for all screened subjects.

A listing of screen failure subjects, inclusion/exclusion criteria assessment and all analysis populations will be presented for all screened subjects.

The number and percentage of subjects who complete the study and who discontinue from the study will be presented by treatment group, gender, and overall, for all screened subjects. The number and percentage of subjects who complete all treatments (HArmonyCA, JUVÉDERM, and BOTOX) and discontinue from any of the treatments (HArmonyCA, JUVÉDERM, and BOTOX) as collected on the CRF will also be presented by treatment group, gender, and overall, for all screened subjects. The primary reason for study discontinuation and treatment discontinuation will be presented as collected on the eCRF. Reasons for discontinuation include:

- Adverse Event
- Lost to Follow-Up
- Pregnancy
- Withdrawal by Subject
- Study Terminated by Sponsor
- Physician Decision
- Protocol Deviation
- Other

A listing of study disposition and treatment disposition will be provided for the Safety Population.

The duration in study (days) will be summarized by treatment group, gender, and overall, for the Safety Population. It is calculated as (Last Assessment Date in the Study – First Assessment Date in the Study) + 1.

A listing of study visits will be provided for the Safety Population.

6.0 Treatment Exposure and Administration

Treatment exposure of HArmonyCa Lidocaine, JUVÉDERM VOLITE, JUVÉDERM VOLBELLA, JUVÉDERM VOLIFT, JUVÉDERM VOLUMA, JUVÉDERM VOLUX will be summarized by visit, point of injection (region/MD code), side, gender, and overall, for the Safety Population. The summaries will include the number of injections and total volume of injections (mL), and average volume of injections (mL).

The average volume of injections (mL) is calculated as total volume of injections (mL) / number of injections.

Treatment exposure of BOTOX will be summarized by visit, point of injection (MD code), side, number of injections, gender, and overall, for the Safety Population.

The investigator is responsible for ensuring that study data is properly recorded in compliance with the protocol at the investigational site.

All treatment exposure data will be listed for the Safety Population.

7.0 Demographics, Baseline Characteristics, Medical History, and Prior/Concomitant Medications/Procedures

7.1 Demographics and Baseline Characteristics

Demographic parameters will be summarized descriptively by treatment group, gender, and overall, for the mITT Population. Demographic parameters include age (years) and sex (if female, childbearing potential).

Baseline characteristics will be summarized descriptively by treatment group, gender, and overall, for the mITT Population. Baseline parameters include height (m), weight (kg), body mass index (BMI) (kg/m²), and Fitzpatrick Skin Type (I, II, III, IV, V, VI).

Demographics and baseline characteristics will be provided in a listing for the Safety Population.

Facial wrinkle scale (FWS) will be collected for glabellar lines (GLs), crow's feet lines (CFLs), and forehead lines (FHLs) at Screening visit. The FWS will be summarized by the severity of each question, by treatment group, gender, and overall, for the Safety Population. FWS data will be provided in a listing for the Safety Population.

